1.3 SCHEDULE OF ACTIVITIES

	Pre-screening (Pre-consent)	Visit 1 Day 1	Visit 2 Day 7±3	Visit 3 Day 14 ±3	Visit 4 Day 21 ±3	Visit 5 Day 28±3	Visit 6 Day 35 ±3	Visit 7 Day 125 ±14	Visit 8 Day 214 ±14	Visit 9 Day 304 ±21	Visit 10 Day 365 ±30
Recruitment / pre-screening	X										
Network pre- screening	X										
Informed Consent		X									
CAPI interview		X						X	X	X	X
HIV testing		X									X
HCV testing		X							X		X
Intervention participation			X	X	X	X	X				
Adverse Events Reporting		X	X	X	X	X	X	X	X	X	X

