Assess network penetration and diffusion among networks of MASLIHAT participants.	80% of MASLIHAT participant network members report conversations about syringe cleaning, condom use, etc.	The MASLIHAT intervention teaches participants to engage in peer education activities	

OBJECTIVES	ENDPOINTS	JUSTIFICATION FOR ENDPOINTS	PUTATIVE MECHANISMS OF ACTION

Assess changes in and mediating effects of HIV knowledge, risk awareness, behavioral norms, and self-efficacy among MASLIHAT participants and their network members compared to the TANSIHAT control condition.
 
Assess the mediating and moderating effects of depression and loneliness among MASLIHAT participants and their network members compared to the TANSIHAT control condition.
			
HIV knowledge, risk awareness, behavioral norms, and self-efficacy are theoretical mediators for intervention effects.
 
Depression and loneliness are indicators of psycho-social well-being that potentially mediates or moderates intervention effects.

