Theoretical mediators. In addition to risk behavior, the questionnaire will assess theoretical mediators including HIV knowledge, risk awareness, behavioral norms, self-efficacy, depression, and loneliness. HIV knowledge is assessed with 16 true/false items; risk awareness is assessed with questions such as "How likely are you to get HIV?" and "How much do worry about HIV?" Behavioral norms⁶⁴⁻⁶⁶ will be assessed with questions such as "How many of your friends who shoot drugs use a needle after someone else, without bleaching or cleaning?" (descriptive norms), and "How many of your friends would disapprove if you shared a needle with a stranger?" (injunctive norms). Responses are given on a 5-point scale from 1 (none) to 5 (all). Self-efficacy for safer drug injection will be measured with six items adapted from the CIDUS-III study⁶⁷ (e.g., "I can avoid sharing a needle even if I am dope sick or in withdrawal"), rated on a four-point scale from "strongly agree" to "strongly disagree". Depression will be measured using the Centers for Epidemiological Studies Depression Scale -- Revised (CESD-R)⁶⁸, and loneliness will be measured using the UCLA Loneliness Scale⁶⁹.

Network penetration & diffusion. Diffusion of MASLIHAT messaging/norms at the network level will be assessed using measures successfully used by SHIELD and other public opinion leadership interventions such as asking network members as to how many (if any) MASLIHAT peer educators they know, whether anyone within their drug using network talked with them about HIV since they were last interviewed, and whether they talked about specific topics (e.g. condom use, syringe cleaning, HIV testing).

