9.4.2 ANALYSIS OF THE PRIMARY ENDPOINT(S)

Relative frequency of syringe sharing, equipment sharing, and vaginal or anal sex without a condom in the past 3 months will be measured at each time point on a 7-point Likert-type scale (Never, Rarely, Less than half the time, About half the time, More than half the time, Most of the time, Always). We will analyze ordinal outcomes, and we will also dichotomize responses to analyze binary (none/any) outcomes.

We will conduct repeated measures mixed effects regressions with random intercepts for subject and recruitment site to test the effect of intervention condition on changes in the outcome variables. We will use ordinal logistic regression for ordinal outcomes and modified Poisson regression for binary outcomes. We will conduct a test of the proportional odds assumption with a likelihood ratio test comparing the proportional odds model with a non-proportional odds model.⁷⁴ We will include the interaction of time and participant type (intervention participant vs. network member) to test for differential effects. If the interaction term suggests differential effects ($p < .10$), we will stratify analyses by participant type. Sociodemographic characteristics (age, education, time in Moscow) will be included as covariates in the analysis if they are related to the outcome at baseline or if they vary significantly across conditions. All participants with at least one follow-up interview will be included in the analysis.

Dosage: If there is variability in attendance, we will estimate repeated measures mixed effect models predicting outcomes with session attendance and the interaction between time, intervention condition, and session attendance as predictors. A significant interaction effect will indicate that the effect of the intervention is moderated by session attendance.

Social Network Diffusion. Additional analyses among network members will examine associations between exposure to intervention concepts (i.e. conversations about health, drugs/alcohol HIV) and changes in outcomes over time.

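### The HIV-conversation item looks back to the previous interview (nominally 124, 89, 90 and 61 days), so reported exposure is not comparable across visits or between men with different attendance

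*Combined protocol and SAP*

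**What the plan says.** Section 8.1 (network penetration and diffusion) gives, as one example of its measures, asking network members "whether anyone within their drug using network talked with them about HIV since they were last interviewed". It goes on to mention specific topics, such as condom use and syringe cleaning, without giving a look-back for them. The primary outcomes in the same section use a fixed three-month recall.

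The Schedule of Activities (section 1.3) places the baseline interview on Day 1 and the follow-up interviews at "Visit 7 Day 125 ±14", "Visit 8 Day 214 ±14", "Visit 9 Day 304 ±21" and "Visit 10 Day 365 ±30". The last group session is at "Visit 6 Day 35 ±3". Section 8.1 counts the follow-ups as 3, 6, 9 and 12 months from the intervention, and section 4.1 spaces them three months apart.

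The conversation data have two uses. Section 3 sets an exploratory endpoint: "80% of MASLIHAT participant network members report conversations about syringe cleaning, condom use, etc", with no visit named. Section 9.4.2 plans to examine, among network members, "associations between exposure to intervention concepts (i.e. conversations about health, drugs/alcohol HIV) and changes in outcomes over time". Neither section mentions the length of the look-back.

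**The concern.** A yes/no report of any conversation since the last interview depends on how often men talk and on how long the window is. If the window differs by visit, a change in the proportion reporting exposure can reflect visit spacing and not diffusion. If it differs between men at the same visit, because of visit tolerances or a missed interview, part of the difference in exposure reflects attendance.

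Section 9.4.2 compares network members by exposure and relates this to change in outcomes over time, so it is open to both effects. The exposure window also does not match the three-month window of the outcomes it is set against. What is at stake is the reading of the diffusion results, which bear on the proposed mechanism of the intervention. No primary or secondary comparison between arms uses this item.

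**Working it through.** **Inputs.** Interview days 1, 125, 214, 304 and 365, with tolerances ±14, ±14, ±21 and ±30 for the follow-ups (section 1.3; none is given for Day 1). The documents give no conversation rate, so one is assumed and varied.

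**Nominal windows.** 125 − 1 = 124; 214 − 125 = 89; 304 − 214 = 90; 365 − 304 = 61 days.

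**Allowed windows.** Adding the tolerances of the two adjacent visits gives 124 ± 14 = 110–138; 89 ± 28 = 61–117; 90 ± 35 = 55–125; 61 ± 51 = 10–112 days.

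**After one missed visit.** Visit 7 missed: 214 − 1 = 213 days at Visit 8. Visit 8 missed: 304 − 125 = 179 days at Visit 9. Visit 9 missed: 365 − 214 = 151 days at Visit 10. Section 7.3 requires two consecutive misses for loss to follow-up and lets absentees rejoin, so such windows will occur.

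**The plan's own timing.** Days after the last session (Day 35) are 90, 179, 269 and 330. Divided by 30.44, these are 2.96, 5.88, 8.84 and 10.84 months. The first three agree with sections 4.1 and 8.1; the fourth falls short of twelve months. Twelve months after Day 35 would be about Day 400, a last window of 400 − 304 = 96 days (91 if a year is taken as 360 days).

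**Effect on reported exposure.** With a constant rate, P(w) = 1 − (1 − P₁₂₄)^(w/124).

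| Visit | Window (days) | P₁₂₄ = 80% | P₁₂₄ = 60% |
|---|---|---|---|
| 7 | 124 | 80% | 60% |
| 8 | 89 | 69% | 48% |
| 9 | 90 | 69% | 49% |
| 10, Day 365 | 61 | 55% | 36% |
| 10, if Day 400 | 96 | 71% | 51% |

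For example, at Visit 10, 1 − 0.20^(61/124) = 0.547.

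Anchoring on a 90-day prevalence gives the same pattern: 20% per 90 days gives 26.5/19.8/20.0/14.0%; 50% gives 61.5/49.6/50.0/37.5%; 80% gives 89.1/79.6/80.0/66.4%; 99% gives 99.8/98.9/99.0/95.6%. The effect shrinks as reporting nears 100%.

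**Effect of a missed visit (P₁₂₄ = 80%).** 1 − 0.20^(213/124) = 94% at Visit 8, against 69% for a regular attender. 1 − 0.20^(179/124) = 90% at Visit 9, against 69%. 1 − 0.20^(151/124) = 86% at Visit 10, against 55%.

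**What would offset it.** A conversation rate 90/61 = 1.48 times that of the preceding window would cancel the fall from Visit 9 to Visit 10. A rate 124/61 = 2.03 times that of the first window would cancel the fall from first to last.

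**The case against.** A reader might infer that reported diffusion must decline from 3 to 12 months whatever men do. The documents do not support that. The second and third windows are practically equal, the allowed windows of the last three visits overlap widely, and a fall requires a constant or declining rate, which is an assumption. If conversation is concentrated in men who talk often while the rest never do, window length matters less than the table shows.

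Much of the size also has a separate source. Of the 25-point fall (80% to 55%), about 14 points (69% to 55%) come from Visit 10 standing at Day 365, which conflicts with sections 4.1 and 8.1. With Day 400 there is one step down after the first follow-up, and then a flat line.

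It is also tempting to say that the 80% endpoint is invalidated, or that background conversation is never measured. Neither follows. The endpoint concerns specific topics whose look-back is not stated, the item is given only as an example, and the questionnaire is not in the documents, so its baseline wording cannot be seen. Section 6.3 applies one instrument to both arms, so control network members supply a concurrent background level. With a common schedule, comparisons between arms at the same visit are not biased, provided attendance is similar.

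Finally, a visit term would absorb the nominal differences in spacing, and 95% of network members in the pilot had complete follow-up. Both points stand in part. No visit term is specified for the diffusion analysis, a visit term does not handle missed or shifted visits, and the pilot followed men for six months, not twelve.

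The first window is itself approximate. Peer delivery starts during training, so somewhat fewer than 124 days can carry intervention talk. Network members, however, are interviewed before their index participant, so their window may be longer: up to about 154 days if the gap reached the 30-day life of the coupon (an assumption).

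**Conclusion.** The concern holds in limited form. The look-back is not fixed, its nominal length halves from the first follow-up to the last (124 to 61 days), it reaches 151 to 213 days after one missed visit, and no adjustment is stated. Exposure reports are therefore not comparable across visits, or between men at the same visit whose windows differ.

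Assuming a constant rate common to all men, and 80% over 124 days, the distortion is 11 points between the first and second follow-ups and 25 points between the first and last as scheduled. With Visit 10 at Day 400, first to last is 9 points. A man back after one missed visit would show 86% to 94%, against 55% to 69% for a regular attender at the same visit.

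The arithmetic concerns the proportion reporting exposure. The direction and size of any bias in the exposure-outcome association are not established. Severity is minor: the endpoint is exploratory and the model is an additional analysis.

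**What to change.** 1. **Section 9.4.2.** Compute days since the previous interview from the recorded dates, and include log(days) together with visit in the diffusion model. This adjusts for window length but does not fully repair an exposure measured over unequal periods; the report should say so.
2. **Reporting.** Give the proportion exposed by visit standardised to 90 days. One way is a complementary log-log model for exposure with log(days/90) as an offset, which is the constant-rate formula above: P₉₀ = 1 − (1 − P_w)^(90/w).
3. **Section 3.** Name one visit at which the 80% target is evaluated, and state the look-back of the topic items.
4. **Sections 1.3, 4.1 and 8.1.** Reconcile the day of Visit 10 with the stated months after the intervention and the stated spacing.
5. **Optional.** Add a version of the item with a fixed three-month recall at baseline and each follow-up. It has two costs. At Visit 7 it reaches back only to about Day 35 (125 − 90), so it misses conversations during the five-week training. At Visit 10 as scheduled it overlaps the previous window by about 29 days (90 − 61). It should therefore sit beside the existing item, which gives continuous coverage, and not replace it.

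Items 1 to 4 need a few lines of text and no added visits or questions. Item 5 adds a short question to each interview.

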8.2 SAFETY ASSESSMENTS

N/A

8.3 ADVERSE EVENTS AND SERIOUS ADVERSE EVENTS

8.3.1 DEFINITION OF ADVERSE EVENTS

Adverse Events (AEs) are defined in this study as “any unfavorable and unintended diagnosis, symptom, sign, syndrome or disease which either occurs during the study, having been absent at baseline, or, if present at baseline, appears to worsen.” An AE may or may not have a causal relationship with the treatment.

Potential AEs:

- violation of confidentiality
- discomfort due to assessment procedures
- embarrassment in disclosing sensitive personal information
- disclosure of information about current and/or intended physical harm to persons
- dissatisfaction with the assessment procedures
- dissatisfaction with the intervention activities
- COVID-19 infection

8.3.2 DEFINITION OF SERIOUS ADVERSE EVENTS

Serious Adverse Events (SAEs) are defined as “any medical occurrence that results in death; is life-threatening; requires inpatient hospitalization or prolongation of existing hospitalization; creates persistent or significant disability/incapacity, or a congenital anomaly/birth defects.” No medical treatment or administering of drugs are a part of this research or its study design, but study participants may be vulnerable to other potential SAEs as shown below.

Potential SAEs:

- death

- life threatening injury or condition
- hospitalization
- persistent or significant disability/incapacity
- adverse attention, action or other negative consequences for a participant that are imposed by Russian authorities as the result of having become knowledgeable of his drug use as a consequence of participation in the study
- other conditions which in the judgment of the investigators represent significant hazards

8.3.3 CLASSIFICATION OF AN ADVERSE EVENT

8.3.3.1 SEVERITY OF EVENT

For adverse events (AEs) not included in the protocol defined grading system, the following guidelines will be used to describe severity.

- **Mild** – Events require minimal or no treatment and do not interfere with the participant's daily activities.
- **Moderate** – Events result in a low level of inconvenience or concern. Moderate events may cause some interference with functioning.
- **Severe** – Events interrupt a participant's usual daily activity and may require systemic drug therapy or other treatment. Severe events are usually potentially life-threatening or incapacitating. Of note, the term "severe" does not necessarily equate to "serious".

8.3.3.2 RELATIONSHIP TO STUDY INTERVENTION/EXPERIMENTAL MANIPULATION

All adverse events (AEs) will have their relationship to study procedures, including the intervention, assessed by an appropriately-trained scientist based on temporal relationship and his/her expert judgment. The degree of certainty about causality will be graded using the categories below.

- **Related** – The AE is known to occur with the study procedures, there is a reasonable possibility that the study procedures caused the AE, or there is a temporal relationship between the study procedures and the event. Reasonable possibility means that there is evidence to suggest a causal relationship between the study procedures and the AE.
- **Not Related** – There is not a reasonable possibility that the study procedures caused the event, there is no temporal relationship between the study procedures and event onset, or an alternate etiology has been established.

OR

- **Definitely Related** – There is clear evidence to suggest a causal relationship, and other possible contributing factors can be ruled out. The clinical event, including an abnormal laboratory test result, occurs in a plausible time relationship to study procedures administration and cannot be explained by concurrent disease or other drugs or chemicals. The response to withdrawal of the

study procedures should be clinically plausible. The event must be pharmacologically or phenomenologically definitive.

- **Probably Related** – There is evidence to suggest a causal relationship, and the influence of other factors is unlikely. The clinical event, including an abnormal laboratory test result, occurs within a reasonable time after administration of the study procedures, is unlikely to be attributed to concurrent disease or other drugs or chemicals, and follows a clinically reasonable response on withdrawal.
- **Potentially Related** – There is some evidence to suggest a causal relationship (e.g., the event occurred within a reasonable time after administration of study procedures). However, other factors may have contributed to the event (e.g., the participant's clinical condition, other concomitant events). Although an AE may rate only as "possibly related" soon after discovery, it can be flagged as requiring more information and later be upgraded to "probably related" or "definitely related", as appropriate.
- **Unlikely to be related** – A clinical event, including an abnormal laboratory test result, whose temporal relationship to study procedures administration makes a causal relationship improbable (e.g., the event did not occur within a reasonable time after administration of the study procedures) and in which other drugs or chemicals or underlying disease provides plausible explanations (e.g., the participant's clinical condition, other concomitant treatments).
- **Not Related** – The AE is completely independent of study procedures administration, and/or evidence exists that the event is definitely related to another etiology. There must be an alternative, definitive etiology documented by the clinician.]

8.3.3.3 EXPECTEDNESS

An AE will be considered unexpected if the nature, severity, or frequency of the event is not expected based on (a) information contained in the protocol, informed consent document, or other research materials; and (b) the characteristics of the subjects, including underlying diseases, behaviors, or traits.

8.3.4 TIME PERIOD AND FREQUENCY FOR EVENT ASSESSMENT AND FOLLOW-UP

The occurrence of an adverse event (AE) or serious adverse event (SAE) may come to the attention of study personnel during study visits and interviews of a study participant, or upon review by a study monitor.

All AEs, not otherwise precluded per the protocol, will be captured on the appropriate case report form (CRF). Information to be collected includes event description, time of onset, assessment of severity, relationship to study procedures, and time of resolution/stabilization of the event. All AEs occurring while on study will be documented appropriately regardless of relationship. All AEs will be followed to adequate resolution.

Any medical or psychiatric condition that is present at the time that the participant is screened will be considered as baseline and not reported as an AE. However, if the study participant's condition deteriorates at any time during the study, it will be recorded as an AE.

The project coordinator will record events with start dates occurring any time after informed consent is obtained until the last day of study participation.

8.3.5 ADVERSE EVENT REPORTING

All research staff and session facilitators will be trained in how to recognize and appropriately respond to an adverse event (AE) should one should occur as part of the study. Staff members will be instructed that such events or incidents must be reported promptly to the Moscow site coordinator and documented using a specially prepared project form, and then reported by the site coordinator ([name]) within 24 hours to Drs. [name], [name], and [name]. They, in turn, will inform NIDA and also the IRBs of the University of Illinois at Chicago (IRB #00009693), the Scientific and Educational Center in Moscow (IRB #00010190) and PRIZMA Research Center (IRB00009927). Further action will be taken under the advisory guidance of the IRBs and NIDA.

8.3.6 SERIOUS ADVERSE EVENT REPORTING

As with AEs, staff members will be instructed any SAE event or incident must be reported promptly to the Moscow site coordinator and documented using a specially prepared project form and then reported within 24 hours by the site coordinator ([name]) to Drs. [name], [name], and [name]. In consultation with the PI, [name] will be responsible for conducting an investigation of a SAE. The PI will report the results of such investigation to the NIDA PO within 3 days and to the UIC, Moscow, and PRIZMA IRBs no later than 5 working days after the investigator first learns of the event. Further action will be taken under the advisory guidance of the IRBs and NIDA.

8.3.7 REPORTING EVENTS TO PARTICIPANTS

N/A

8.3.8 EVENTS OF SPECIAL INTEREST

The project coordinator will monitor session attendance and follow-up interview participation, and record any instances of arrest or deportation whether or not associated with study participation. Incarceration of a research participant will be reported to the UIC IRB.

8.3.9 REPORTING OF PREGNANCY

N/A

8.4 UNANTICIPATED PROBLEMS

8.4.1 DEFINITION OF UNANTICIPATED PROBLEMS

This protocol uses the definition of Unanticipated Problems as defined by the Office for Human Research Protections (OHRP). OHRP considers unanticipated problems involving risks to participants or others to include, in general, any incident, experience, or outcome that meets all of the following criteria:

- Unexpected in terms of nature, severity, or frequency given (a) the research procedures that are described in the protocol-related documents, such as the Institutional Review Board (IRB)-approved research protocol and informed consent document; and (b) the characteristics of the participant population being studied;
- Related or possibly related to participation in the research (“possibly related” means there is a reasonable possibility that the incident, experience, or outcome may have been caused by the procedures involved in the research); and
- Suggests that the research places participants or others at a greater risk of harm (including physical, psychological, economic, or social harm) than was previously known or recognized.

